Over 80% of patients with lateral epicondyle tendinopathy report improvement within 1 year, which supports the often adopted wait-and-see policy.^[7] Within this period, workload and activity modification is recommended to remove any exacerbating stimulus, relieve strain and allow time for healing.^[12] Topical non-steroidal anti-inflammatory drugs (NSAIDs) may provide beneficial relief from pain compared with placebo in the short term (3-4 weeks)^[13-16]. Oral NSAIDs have not been found to provide longer-term effects (> 4 weeks), however the risk of gastro-intestinal adverse effects is significantly increased.^[13-17] The Cochrane review of NSAIDs for treating lateral elbow pain concludes that evidence on which to base recommendations for the longer-term use of NSAIDs is insufficient.^[14] Local corticosteroid injections have been found to provide beneficial short-term therapeutic effect (< 6 weeks), however this was not continued into the intermediate (6 weeks to 6 months) or longer (> 6 months) terms.^[15,18-19] Biset *et al.* found corticosteroid injection to be superior compared with physiotherapy at 6 weeks, however high reoccurrence rates were observed (47 of 65 patients deemed initial successes subsequently represented), and long term outcomes were found to be significantly poorer compared with physiotherapy.^[20] Adverse effects include: post-injection pain, skin depigmentation, subcutaneous fat atrophy, and, in some instances, tendon and ligament rupture.^[21,22]

HYALURONIC ACID

Hyaluronic acid (HA) is a naturally occurring polymer, ubiquitous to the human body. HA, in its aggregated form, is an important structural component of the articular cartilage matrix, imbibing water molecules to provide cartilage resilience to compressive forces. Unaggregated, HA is the main macro-molecular constituent of synovial fluid and is fundamental to its characteristic viscoelastic properties. This enables the intra-articular fluid to function as a lubricant and a shock absorber between congruent cartilaginous surfaces. HA does not only

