During the procedure the patient will be distracted by being asked to confirm their personal details.

Patients will be given pain report diaries which will be completed on days 1, 2, 3, 7, and 14, and at 6 weeks, 12 weeks (final clinical follow up visit prior to discharge).-Patients will be taught home exercises by a blinded physiotherapist prior to discharge, a formal class based physiotherapy programme will commence at 5-15 days post injection. The patient will be assessed by a blinded clinician at 3 months and 12 months post treatment. Telephone follow-up calls will be made to patients 3 months and 12 months post treatment if the patient declines to attend a follow-up appointment. The Consulting physician will discharge patients from his direct care at 12 weeks unless enduring or subsequently manifesting symptoms persist. Pain scores, amount of rescue medication (codeine & Paracetamol) and QOL questionnaires will be completed at all visits. The OES, qDASH, HAD and EQ5D will be completed at 3 and 12 month reviews.

Patients who successfully complete both 3 month and 12 months outcome questionnaires with be entered into a raffle to win an iPad tablet computer.

Primary Measure of Outcome.

The difference in Objective Functional Assessment as evinced by Quick DASH, at 12 months

Secondary Measures of Outcome.

The difference in Objective Pain and Functional Assessment as evinced by OES and 100 point VAS with terminal descriptors at 12 months

Change in EQ5D General Health Questionnaire.

Relationship of pre-injection HAD score to outcome.

Change in HAD score at 12months

Use of Rescue Medication.

Number of Patients.

The proposed randomized controlled double blind (single centre) trial design will have 80% power (1- β) to reject the null hypothesis, with an α (type I error, i.e. level of statistical significance) set at 0.05. Assuming a clinically significant [mean] difference (δ) of 15 Q-DASH score units between groups together with an estimated sample standard deviation (σ) of 22.5 (Biomet study – based on Q-DASH score for PRP arm) which gives an 'n' for each trial arm (assuming equal group sizes) of at least 35 analyzable patients in each of the three groups (A,B &C) and given a possible attrition rate of about 16% the CITTE trial will probably therefore need a total sample size of at least 123 of patients, approximately.

Statistical Analysis.

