All quantitative data - age, gender, duration of symptoms, disease progression, target joint, Height, weight and BMI, will be analysed using the most appropriate non-parametric tests. VAS, qDASH and OES score Inventories, EQ5D, Blinded Assessor and escape medication scores will be tested for homogeneity of variance (Chi sq/F test), mean scores calculated, and then either *t* tested (with possible ANOVA for correlations between pain, function, strength etc) or Mann-Whitney/ Wilcoxon rank sum (Kruskall Wallis differences /Jonkheere trend).

Interventions

Physiotherapy protocol

After the injection and prior to discharge a physiotherapist will teach patients eccentric loading exercises of the wrist extensors. They will be instructed to commence the exercises at day 1 post injection. They will be advised to carry out 3 sets of 15 repetitions, 3 times per day. An accompanying exercise sheet will advise to increase the load as symptoms permit. It will be suggested to commence with a half filled 500ml bottle of water. In addition a simple common extensor stretch will be taught to use following the eccentric exercises.

At 5-15 days post injection the patients will commence an out-patient class based physiotherapy programme. The class will be held 2 weekly by a blinded physiotherapist. After being taught the exercises on an 1:1 basis, the patients will be supervised during a circuit style exercise programme. The exercise programme will include eccentric loading of the common extensors, and upper limb strengthening involving the full kinetic chain, in particular the rotator cuff and scapular muscles. Each patient will be supervised and monitored to improve technique, and to increase the load. Patients will be provided with a home exercise programme which will reflect the class exercises.

Study GROUP A Product Dose, Presentation, and Mode of Administration.

2ml unbuffered PRP prepared with **Zimmer/Biomet Recover Mini-platelet** system administered via intratendinous injection under ultrasound.

Study GROUP B Product Dose, Presentation, and Mode of Administration.

Ostenil[™] Tendon (40mg/2ml of bio-fermentation source Sodium Hyaluronate with 10mg Mannitol in a pre-filled syringe). To be administered via peritendinous injection under ultrasound.

Licensed indication in the EU: For the treatment of pain and restricted mobility in tendon disorders.

Active Ingredient; Sodium Hyaluronate / Mannitol

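### On its natural reading, a variance pre-test chooses between a t test and a rank test for 12-month Quick DASH, and sends unequal-variance data to a test that does not compare means

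*Combined protocol and SAP*

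**What the plan says.** The protocol's Primary Measure of Outcome is "The difference in Objective Functional Assessment as evinced by Quick DASH, at 12 months". Number of Patients states that the design "will have 80% power (1- β) to reject the null hypothesis", with the "level of statistical significance) set at 0.05". It assumes a clinically significant mean "difference (δ) of 15 Q-DASH score units between groups" and an "estimated sample standard deviation (σ) of 22.5", taken from a PRP arm and applied to all three arms, and arrives at 35 analysable patients per arm.

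Statistical Analysis is the only text on how the outcome is compared. The listed scores, qDASH among them, "will be tested for homogeneity of variance (Chi sq/F test), mean scores calculated, and then either" t tested "or Mann-Whitney/ Wilcoxon rank sum (Kruskall Wallis differences /Jonkheere trend"). The variance test is the only criterion named before the choice. The section gives no significance level for that test, no unequal-variance method and no single primary test.

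**The concern.** Three things look wrong.

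- **The outcome data choose the method.** The sentence order (variance test, then one analysis or the other) makes the primary method depend on a preliminary test of the outcome itself.
- **The routing goes the wrong way.** If two arms have equal means but different spreads, particularly with skewed scores, a rank-sum test can reject more often than its nominal level. It is sensitive to differences in distribution other than the mean. The usual remedy for unequal variances, when the target is a difference in means, is an unequal-variance comparison.
- **The rank test gives no interval for the target.** The trial is sized on 15 Quick DASH points. A rank-sum p-value has no confidence interval for a mean difference that could be read against 15.

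At stake are the error rate of the primary comparison and whether its result is expressed on the scale used to size the trial.

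**Working it through.** **The plan's own figure.** For two means, two-sided 0.05 and 80% power (the protocol does not state sidedness):

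n = 2 × (1.960 + 0.842)² × (22.5/15)² = 2 × 7.85 × 2.25 ≈ 35.3 per arm.

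The stated 35 agrees with this to within rounding. One-sided testing would give 28. Inflating, 35 × 1.16 = 40.6, rounded up to 41, and 41 × 3 = 123, as stated. So the sample size is built on a two-sided comparison of two means.

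**The check.** Two-arm trials were simulated with 35 per arm and equal true means. A two-sided F test at an assumed 0.05 selects Mann-Whitney if it rejects and the pooled t test if it does not. Welch's test is applied throughout for comparison.

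- From the protocol: 35 per arm and SD 22.5.
- Assumed: the F-test level, the score shapes, the means and the smaller SDs.
- Skewed scores are beta-distributed on 0-100. With mean m and SD s as fractions, k = m(1−m)/s² − 1, and the parameters are mk and (1−m)k. For mean 20 and SD 22.5, k = 0.16/0.0506 − 1 = 2.16, giving parameters 0.43 and 1.73.

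Rejection rates under equal means, 40,000 trials per row (standard error about 0.1 point near 5%):

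| Scores | SDs | Sent to rank test | Rank test alone | Whole rule | Welch |
|---|---|---|---|---|---|
| Normal | 22.5 / 22.5 | 5.1% | 4.8% | 4.9% | 4.8% |
| Normal | 22.5 / 15 | 64.5% | 5.1% | 5.1% | 4.9% |
| Normal | 22.5 / 11.25 | 97.7% | 5.8% | 5.8% | 4.9% |
| Skewed, mean 25 | 22.5 / 22.5 | 6.2% | 5.1% | 4.2% | 5.1% |
| Skewed, mean 25 | 22.5 / 18 | 25.7% | 8.0% | 4.4% | 5.0% |
| Skewed, mean 25 | 22.5 / 15 | 64.2% | 12.5% | 8.1% | 5.2% |
| Skewed, mean 25 | 22.5 / 11.25 | 97.2% | 18.8% | 18.3% | 5.2% |

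Further runs of 20,000 trials on skewed scores (ranges cover repeat runs):

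- Mean 20, SDs 22.5 / 15: 62% go to the rank test, which rejects 21%. The whole rule rejects 11.3-11.8%, Welch 5.0-5.5%.
- Mean 20, SDs 22.5 / 12: rule 27.6-28.2%, Welch 5.3-5.4%.
- Means 30 to 35, SDs 22.5 / 15: rule 5.9-6.9%.
- Mean 20, identical arms: the F test declares unequal variances in 11%, but the rule rejects only 3.6%.

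**Unequal arms.** With a 30/40 split, SD ratio 2 and the larger SD in the smaller arm, the rule rejects 6.9% (normal) and 19.6% (skewed, mean 25). The pooled t test rejects 7.4% and 7.7%, and Welch 5.1% and 5.5%.

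**Power for a true 15-point difference, 35 per arm.** With normal scores and SD 22.5 in both arms, Welch has 78.4% and the rule 78.3%. With skewed scores, means 35 and 20 and SD 22.5 in both arms, the rank test has 89.5%, Welch 77.6% and the rule 78.4%.

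**The case against.** **The rule is inferred.** The sentence gives no threshold and never says that unequal variances lead to Mann-Whitney; it may only list candidate methods. This stands as a limit on how firmly the point can be put. It does not rescue the plan: if the variance test does not decide, nothing does. The primary test is then chosen after the data are seen, and the same edit cures it.

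**A reader might infer that the type I error is simply not 0.05.** The documents do not support that. They give one SD, no expected means and no score shape, and several plausible scenarios show no inflation. Clear inflation needs marked skew and an SD ratio of about 1.5 or more. Skew is plausible, since Treatment Options reports "Over 80% of patients with lateral epicondyle tendinopathy report improvement within 1 year". But that describes patients in general, and improvement is not a score near zero. This trial enrols referred patients with symptoms beyond 3 months and excludes pain scores below 4/10.

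**In the worst case the distributions really differ.** At SDs 22.5 and 12 the medians are about 11 and 18, so rejecting is an error only if the null is equal means. The protocol does not spell out its null hypothesis, but it sizes the trial on a mean difference, which makes equal means the natural one.

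**A reader might infer that the rank branch would report only a p-value.** The text has mean scores calculated before either branch. What the rank test lacks is an interval for the mean difference.

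**A reader might take disagreement between the t and rank tests as an effect of the pre-test.** It is not. In the skewed 15-point scenario (means 35 and 20), the rule's verdict differs from the t test's in only 0.8% of trials.

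**The pooled t test does nearly as well at equal n.** This is true: it held 4.8-5.5% in the equal-arm, equal-means scenarios, so dropping the rank branch does most of the work. Welch earns its place when attrition leaves the arms unequal.

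**Conclusion.** The point holds on the natural reading of Statistical Analysis, and the remedy covers the other reading too. A trial sized on a 15-point mean difference should not let a variance test route its primary outcome to a test that, in exactly that circumstance, no longer tests equal means.

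The size is conditional. The rule is close to nominal for normal scores (about 5-6%) and slightly conservative for skewed scores with equal or mildly unequal SDs (about 4-5%). It is inflated to about 6-12% for skewed scores with SDs 22.5 and 15, as the common mean falls from 35 to 20, and to 28% in the most extreme case examined. Welch's test stays at about 5-5.5% throughout. These figures rest on the assumed F-test level, score shapes, means and smaller SDs, and on two-arm comparisons; the three-arm Kruskal-Wallis and Jonckheere options were not simulated. The stated sample size is not in question here.

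**What to change.** Delete the variance pre-test from Statistical Analysis. State that 12-month Quick DASH is compared, for each pair of arms the trial compares, as a difference in means with a 95% CI, using Welch or robust standard errors whatever the observed variances, and is read against 15 points. Treat OES, VAS and EQ5D likewise. Keep the rank tests as labelled sensitivity analyses.

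The cost is one rewritten sentence and almost no power when variances are equal (78.4% against 78.3% above). The real downside is that a rank test can be more powerful for skewed scores (about 90% against 78% in the scenario with means 35 and 20), though it answers a different question. The edit does not settle which pairs of arms are primary, multiplicity or baseline adjustment; those are separate matters.

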Hart et al. conducted a meta-analysis of 41 studies to determine the efficacy and risk of adverse effects of peritendinous corticosteroid and other injection therapies in the management of tendinopathy.^[38] Hart concluded that corticosteroid injection is beneficial in the short term for the treatment of tendinopathies but may be worse than other treatments in the intermediate and long terms, and that no clear evidence of benefit of other injections was shown, except for HA in the short and long terms. Saito et al. conducted a meta - analysis into therapeutic effects of subacromial HA injection in patients with chronic shoulder pain.^[39] 19 randomised controlled trails were included totalling 2,120 patients. The study concluded that HA injection is effective for the relief of pain and is a safe alternative to corticosteroid injection for chronic painful shoulder. Ostenil[™] (HA) has been shown to substantiate these findings in patients presenting with primary subacromial impingement syndrome, with Funk *et* al concluding "HA appears to be as effective as depomedrone in reducing subacromial impingement pain but does not produce the pain surge associated with depomedrone in the first 72 hours post-injection."^[40]

Petrella *et al.* evaluated the treatment of 331 competitive racket sport athletes with chronic lateral epicondyle tendinopathy (> 3 months) in a double-blind, randomised, placebo-controlled trail over a one year period.^[41] 2 subcutaneous injections were administered, of either1% Sodium Hyaluronate (SH) or saline injection: the first injection at baseline evaluation, the second one week later. Post-injection care of rest, ice, compression, and elevation was instructed and no formal adjunct physiotherapy was prescribed. VAS pain at rest significantly improved in the HA group compared with control, which corresponded to a statistically significant improvement in maximal grip strength. These differences persisted at the 90-day and 365-day follow-up appointments. Time to return to pain-free and disability-free sport was 18 days in the HA group, but was not achieved at any time point within the study in the control group.

Ostenil Tendon[™], a novel, patented 2% concentration of fermentative source HA with the addition of Mannitol has previously been shown to relieve pain and improve function in patients with partial thickness tears of the supraspinatus tendon and in patients with Achilles, lateral epicondyle and peroneal tendinopathies.^[42, 43]

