PLATELET-RICH PLASMA

Platelet-rich plasma (PRP) describes an autologous blood plasma fraction, enriched with platelets, thus presenting a high concentration of protein growth factors. The extracted and prepared fluid is injected at the sight of tendon injury, theoretically acting as an adjuvant to complement and promote the natural healing process. The use of PRP in the management of musculoskeletal injuries has increased, based on in vitro studies reporting an enhancement of the recruitment, proliferation, and differentiation of the cells involved in muscular tissue regeneration.^[44]

PRP exerts it effects via the degranulation of the α -granules in platelets, which release various fundamental growth factors and cytokines; active secretion is initiated by the blood clotting process and begins within 10 minutes of clotting.^[45] As the platelets are activated, the growth factors are secreted from the cell through the cell membrane, the secreted growth factors immediately bind to the external surface of cell membranes within the wound, and in turn induce an activation of an endogenous internal signal protein, which causes the expression of a specific gene sequence of the cell such as cellular proliferation, matrix formation, osteoid production, or collagen synthesis.^[44]

Mishra *et al.* evaluated 140 patients with lateral elbow tendinopathy; patients had initially undergone a standardised physical therapy protocol and a variety of nonsurgical treatments. 20 patients experienced persistent pain and failed to respond adequately, this cohort were then given either a single percutaneous injection of platelet-rich plasma or bupivacaine as a control.^[48] Eight weeks post-injection, the study group reported a 60% improvement in pain

compared with a 16% improvement in the control group. At six months response within study group had increased to 80% improvement.

De Vos *et al.* recently published a systematic review of PRP injections for chronic lateral epicondyle tendinopathy.^[46] Five of the six studies included found no significant benefit in the study group compared with their respective controls at follow-up. The final study showed a beneficial effect compared with corticosteroid injection.

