Consenting participants will be randomised to Study Group A (physio and PRP), Study Group B (physio and Ostenil Tendon[™]), or Control Group C (physio and sham injection) once informed consent has been recorded and baseline data has been collected.

Treatment and follow-up will be the same for those patients who wish to take part in the study and for those patients who decline to take part but whose condition makes a peri-tendinous injection clinically appropriate. Following informed consent, patients will be assessed for demographic detail (age, gender, ethnicity, occupation, affected elbow, height and weight/BMI, duration of symptoms, relevant diagnosis, current medication), and given patient completed questionnaires to assess pain and function (Oxford Elbow Score (OES), Quick DASH Score, 100 mm visual analogue pain scale with terminal descriptors), Hospital Anxiety and Depression (HAD) Score and asked to complete EQ5D at the initial consultation (V1).

Treatment: Consenting patients will attend for the injection to be administered under ultrasound guidance. All participants will have 30ml of whole venous blood withdrawn under aseptic conditions.

Out of sight of the patient the whole venous blood will either be;

placed in the cell separator and centrifuged at 32000 rpm for 15 minutes for subjects in group A. During the centrifugation process 2ml of 2% plain lidocaine will be injected into the subcutaneous layer at the site of injection of the PRP. One millilitre (2ml) of PRP produced will be drawn into a syringe wrapped in silver foil and injected under ultrasound control via a blue (20 gauge) hypodermic needle into the lateral epicondyle using a peppering technique.

Or

discarded for those in group B and C. The centrifuge will be set to run at 32000rpm for 15 minutes with a saline counterbalance. During the centrifugation process 2ml of 2% plain lidocaine will be injected into the subcutaneous layer at the site of injection. For those in group B a pre-prepared "Ostenil Tendon" syringe will be wrapped in silver foil and 2ml will be injected into the peri-tendinous area via a blue (20 gauge) hypodermic needle under ultrasound control.

For those in group C an empty syringe wrapped in silver foil with a blue (20 gauge) hypodermic needle will be used to perform a sham injection into the subcutaneous tissue only by passing the needle into the tissue with no injectate.

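### A Jonckheere trend test is listed for three arms that have no natural order, and the plan sets none; its result would turn on that unset order

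*Combined protocol and SAP*

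**What the plan says.** The Statistical Analysis section gives one list of methods for the VAS, Quick DASH, OES, EQ5D, blinded-assessor and rescue-medication scores. After a check of variances they are to be compared either by t test (with a possible ANOVA) or by Mann-Whitney/Wilcoxon rank sum, followed in brackets by "Kruskall Wallis differences /Jonkheere trend". Quick DASH at 12 months is the primary outcome, so the trend test is an allowed analysis of it. The section does not say when the trend test applies, in what order it takes the groups, whether it is one- or two-sided, or which listed test is primary.

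The arms are defined under Procedure: "Consenting participants will be randomised to Study Group A (physio and PRP"), Group B receives physiotherapy with hyaluronate, and Group C physiotherapy with sham. The title, the Aim and the closing statement of the Background name the injections in a different sequence: hyaluronate, PRP, sham. None of these sequences is presented as an expected ranking.

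**The concern.** Jonckheere's test looks for scores that rise or fall steadily across groups in a prespecified sequence, such as increasing doses. Here the groups are two different products and a sham. Sham has an obvious place at one end, but nothing fixes PRP relative to hyaluronate.

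The Background does not fix it either. On injections other than corticosteroid it cites a meta-analysis in which "no clear evidence of benefit of other injections was shown, except for HA in the short and long terms". Of a systematic review of PRP it says "Five of the six studies included found no significant benefit in the study group compared with their respective controls at follow-up". It also cites a small PRP study with 60% improvement against 16% in controls at eight weeks. A result in which only one product works is therefore realistic, and it could be either product.

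Three things are at stake. With the wrong order the test has almost no power. With the order chosen after the data are seen, it is no longer a 5% test. And a significant trend does not say which injection differs from sham.

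**Working it through.** **Inputs (Number of Patients section).** Alpha: "level of statistical significance) set at 0.05", sidedness not stated. Power: "will have 80% power". Difference: "of 15 Q-DASH score units between groups", with the pair of arms not named. SD: "of 22.5 (Biomet study" being the cited source. Analysable patients: 35 per arm.

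**Step 1. The plan's own figure.** n = 2 × [22.5 × (1.960 + 0.842) / 15]² = 35.3 per arm, which matches 35. Power at 35 is 79.6% by the normal approximation and 78.5% by the noncentral t. A one-sided 5% test would need only 28, so two-sided 5% is used below.

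**Step 2. Why the order matters.** The Jonckheere statistic J adds, over the three pairs of arms, the number of patient pairs in which the later arm has the higher score. With n = 35 per arm there are 35² = 1,225 patient pairs for each pair of arms. With no true difference:

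- mean of J = 3 × 1,225 × 0.5 = 1,837.5
- variance of J = [105² × 213 − 3 × 35² × 73] / 72 = 28,889.6, so the SD is 170.0

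Suppose hyaluronate alone improves the score by 15 points, taking lower as better (the sign does not affect a two-sided test). A sham or PRP patient then scores above a hyaluronate patient with probability p = Φ(15 / (22.5 × √2)) = Φ(0.471) = 0.681.

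- Order A-B-C: mean of J = 1,225 × [(1 − 0.681) + 0.5 + 0.681] = 1,837.5, exactly the null mean. The A-B and B-C contributions cancel, so more patients do not help.
- Order B-A-C: mean of J = 1,225 × [0.6813 + 0.6813 + 0.5] = 2,281.7. The shift is 444.2 / 170.0 = 2.61 null SDs, which gives power of roughly Φ(2.61 − 1.96) = 74%.

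**Step 3. Simulation.** Normal scores, SD 22.5 in every arm, 35 per arm, large-sample Jonckheere z, two-sided 5%, 100,000 trials per row:

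| True benefit over sham | Jonckheere A-B-C | Jonckheere B-A-C | Kruskal-Wallis |
|---|---|---|---|
| none | 5% | 5% | 5% |
| hyaluronate 15, PRP 0 | 4% | 76% | 80% |
| PRP 15, hyaluronate 0 | 76% | 4% | 79% |
| hyaluronate 15, PRP 7.5 | 25% | 77% | 66% |
| both 15 | 76% | 76% | 80% |

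In the second row the hyaluronate v sham comparison has power of 78% by t test and 76% by Mann-Whitney. In a separate run of that row with 41 per arm (123 / 3), Jonckheere in A-B-C order still rejected in 3.9%.

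**Step 4. Type I error if the choice is left open.** Three arms allow three distinct orders for a two-sided test, since reversing an order changes nothing. With no true difference, taking the most significant of the three rejects in about 12%. Keeping A-B-C fixed but counting success if either Kruskal-Wallis or Jonckheere is significant rejects in 7.0% to 7.6% across separate runs.

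**The case against.** The strongest reply is that Jonckheere is only one item in a list. The same sentence names the t test, Mann-Whitney and Kruskal-Wallis, and each would find a lone 15-point hyaluronate effect with about 75% to 80% power. A reader might infer from the 4% that the trial would almost never detect a real hyaluronate effect. The documents do not support that. It would require the trend test to be the deciding test, the order to be A-B-C, and PRP to be about equal to sham. The plan states none of these. A-B-C is merely the label order; the title and Aim give hyaluronate first, and in that order the power is 76%. This objection stands against the stronger reading. It does not justify keeping the test, because the plan names no primary test and so nothing stops the trend test from deciding or from being the one reported.

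A reader might also infer that the false-positive rate is 12%. That holds only if the order is picked after the data are seen. The plan does not propose this; it only fails to exclude it.

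Finally, the sentence does not say outright that the trend test compares arms, and the secondary outcomes include the relation of baseline HAD score, an ordered measure, to outcome. A trend test could have a use there, although the plan does not state one. This limits the deletion to the comparison of arms.

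**Conclusion.** The point holds as a wrong item in the list of analyses for the primary outcome. The arms are unordered, no order is set, and two sequences found in the protocol lead to opposite results: about 4% against 76% power when one product alone works, with the sequence that fails depending on which product it is. Kruskal-Wallis gives about 80% in either case and needs no order. In A-B-C order the loss shrinks as PRP approaches hyaluronate in effect (25% power at half the effect, 76% at equal effect), but a significant trend still does not identify the effective injection. Leaving the choice open carries a type I error of about 12% for a post hoc order, or about 7% to 8% for accepting either three-arm rank test.

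The figures rest on normal scores, a common SD of 22.5, 35 analysable patients per arm and two-sided 5% testing. Normality, equal SDs and sidedness are assumptions that the protocol does not state. The finding that no order exists or is specified rests on none of them.

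**What to change.** In the Statistical Analysis section, delete the Jonckheere trend test as a comparison of arms. If a rank analysis is used, make it Kruskal-Wallis followed by pairwise Mann-Whitney comparisons. The protocol currently names no pairs, so it must list them: PRP v sham, hyaluronate v sham, and PRP v hyaluronate. With three arms, testing each pair at 5% only after a significant Kruskal-Wallis test at 5% keeps the familywise error at 5%, because any two of the pairwise null hypotheses together imply the null for all three arms. The same revision should state which test is primary for Quick DASH at 12 months. If a trend test is wanted for the HAD question, it should be written under that outcome with its ordering stated.

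The cost is two words removed and a sentence or two added before unblinding. No patients or data items are added. Nothing is lost in the comparison of arms, because the arms are not an ordered factor.
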